## Appendix A

|  |   |  |
|--|---|--|
| 2
A minimum of 2 moderate (S02) or 1 severe (S03) vertebral fragility fractures
[radiographic evidence of at least two moderate (ie, a reduction in vertebral body height of 26–40%) or one severe (more than 40% reduction) prevalent vertebral fragility fracture]   | 
Measured from enrollment to 90 days prior to the day of drug initiation in inpatient or outpatient care setting (any position):
 
Vertebral Fractures diagnosis:
ICD9 diagnosis codes: 805.x, 806.x, 733.13
ICD10 diagnosis codes: M48.4, M48.5, M80.x, S12.x, S22.x, S32.x
 
Vertebral fracture procedures:
HCPCS codes: 22305, 22310, 22315, 22318, 22319, 22325–22328, 22510–22515, 22520–22525, 27200, 27202, 72291, 72292, 76012, 76013, 77082, 77085, 77086, S2360–S2363
ICD10 px: OPQ3xx, OPQ4xx, OPR3xx, OPR4xx, OPS3xx, OPS4xx
ICD-9 px: 03.53
  | 
NB. We excluded patients with diagnosis of vertebral fractures from 89 days prior to and including the day of drug initiation to increase the probability of measuring incident vertebral fractures and not prevalent vertebral fractures. The 90-day gap is described in: Wright NC, Daigle SG, Melton ME, Delzell ES, Balasubramanian A, Curtis JR. The Design and Validation of a New Algorithm to Identify Incident Fractures in Administrative Claims Data. J Bone Miner Res. 2019 Oct;34(10):1798–1807. doi: 10.1002/jbmr.3807.
 |
| 3
AP lumbar spine or total hip or femoral neck BMD $\geq$ 1.5 SD below the average BMD for young healthy, non-Hispanic, Caucasian women (T-score $\leq$ –1.5 SD).   | 
Measured start of all available data and including day of drug initiation in inpatient or outpatient care setting (any diagnosis position):
 
Osteoporosis diagnosis
ICD-9 diagnosis: 733.00, 733.01, 733.02, 733.03, 733.09, 733.13
ICD-10 diagnosis: M81.0, M81.6, M81.8, M80.88*, M80.00*, M80.01*, M80.02*, M80.03*, M80.04*, M80.05*, M80.06*, M80.07*, M80.08*
 
OR
 
Osteoporosis treatments:
Alendronate, Ibandronate, Risedronate, Etidronate, Tiludronate, Denosumab, Calcitonin, Romosozumab, Raloxifene, ZA, Pamidronate (reported as osteoporosis drug in the VERO trial)
  |  |
| 4
Without language barrier, cooperative, able to come to the clinic for all follow-up visits; has given informed consent before entering the study and after being informed of the medications and procedures to be used in this study.   | N/A   |  |
| 5
In the opinion of the investigator, is willing to be trained and to use the pen injector daily, is able to satisfactorily use a pen-type injection delivery system, or is willing to receive daily subcutaneous injections from a caregiver who has been trained to use the pen injector.   | N/A   |  |
| EXCLUSION CRITERIA  |   |  |
| 1.1
Increased baseline risk of osteosarcoma. This includes patients with Paget's disease of the bone [...]. As elevation of serum alkaline phosphatase activity may indicate the presence of Paget's disease, an unexplained elevation of this enzyme activity will also be exclusionary.   | 
Measured 365 days prior to and including the day of drug initiation in inpatient or outpatient care setting (any diagnosis position):
 
ICD-9 diagnosis: 731.0 Osteitis deformans without mention of bone tumor (Paget's Disease)
ICD-10 diagnosis: M88.xxx Osteitis deformans [Paget's disease of bone]
 
+ Tiludronate (exclusion criteria 21.1)
   |  |
| 1.2
[...] previous primary skeletal malignancy, or skeletal exposure to therapeutic irradiation.  | Captured in criteria 13   |  |
| 2
History of unresolved skeletal diseases that affect bone metabolism, other than osteoporosis, including renal osteodystrophy, osteomalacia, hyperparathyroidism (uncorrected), hypoparathyroidism, and intestinal malabsorption.  | 
Measured 365 days prior to and including the day of drug initiation in inpatient or outpatient care setting (any diagnosis position):
 
Renal osteodystrophy
ICD-9 diagnosis: 588.0
ICD-10 diagnosis: N25.0
 
Osteomalacia
ICD-9 diagnosis: 268.2
ICD-10 diagnosis: M83.x
 
Cushing syndrome and disorders of adrenal glands:
ICD-9 diagnosis: 255.xx
ICD-10 diagnosis: E24.x
 
Hyperparathyroidism and hypoparathyroidism:
ICD-9 diagnosis: 252.x, 588.81
ICD-10 diagnosis: E21.x, E20.x, N25.81
 
Intestinal Malabsorption:
Celiac disease, Tropical sprue, Pancreatic steatorrhea, Non-celiac gluten sensitivity, Malabsorption due to intolerance elsewhere classified, Whipple's disease, Other intestinal malabsorption
ICD-9 diagnosis: 579.xx, 040.2
ICD-10 diagnosis: K90.xx
 |  |
| 3
Abnormally elevated values of serum albumin-corrected calcium levels at baseline, defined as $\geq$ 10.6 mg/dL (or $\geq$ 2.65 mmol/L). In cases with borderline non-eligible values ( $\geq$ 10.6 and $\leq$ 10.7 mg/dL), a re-test would be allowed during the screening period.  | 
Measured 30 days prior to and including the day of drug initiation in inpatient or outpatient care setting (any diagnosis position):
 
Hypercalcemia and Hypocalcemia:
ICD-9 diagnosis: 275.41, 275.42
ICD-10 diagnosis: E83.51, E83.52
  |  |
| 4
Abnormally low values of serum albumin-corrected calcium levels at baseline, defined as $<$ 8.0 mg/dL (or $<$ 2.0 mmol/L). In cases with borderline non-eligible values ( $>$ 7.8 to $<$ 8.0 mg/dL), a re-test would be allowed during the screening period to allow normalization with vitamin D and calcium supplements before the randomization visit. | see Criteria 3  |  |

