### 5.3 Flowchart of the study cohort assembly

For teriparatide vs. risedronate

|  | Optum CDM         |                    | IBM® MarketScan®  |                    |
|--|-------------------|--------------------|-------------------|--------------------|
|  | Excluded Patients | Remaining Patients | Excluded Patients | Remaining Patients |
| All patients   |                   | 78202636           |                   | 200203908          |
| Did not meet cohort entry criteria   | -77830806         | 371830             | -199450502        | 753406             |
| Excluded due to insufficient enrollment  | -90897            | 280933             | -176733           | 576673             |
| Excluded due to prior use of referent  | -199055           | 81878              | -403827           | 172846             |
| Excluded due to prior use of exposure  | -19897            | 61981              | -44254            | 128592             |
| Excluded because patient qualified in >1 exposure category   | 0                 | 61981              | 0                 | 128592             |
| Excluded based on Inclusion criteria #1 - Age >= 45  | -1814             | 60167              | -3865             | 124727             |
| Excluded based on Inclusion criteria #2 - Female   | -4439             | 55728              | -9140             | 115587             |
| Excluded based on Inclusion criteria #3.1 - History of vertebral fracture (including from inception to 90 days)      | -48548            | 7180               | -103348           | 12239              |
| Excluded based on Inclusion criteria #3.2 - Vertebral fracture diagnosis excluded in the 90 days before cohort entry | -740              | 6440               | -969              | 11270              |
| Excluded based on Inclusion criteria #4 - Osteoporosis   | -3                | 6437               | -18               | 11252              |
| Excluded based on Exclusion criteria #1 - Pregnancy  | -1                | 6436               | -1                | 11251              |
| Excluded based on Exclusion criteria #2 - Paget's Disease  | -5                | 6431               | -9                | 11242              |
| Excluded based on Exclusion criteria #3.1 - Renal Osteodystrophy   | -2                | 6429               | -1                | 11241              |
| Excluded based on Exclusion criteria #3.2 - Osteomalacia   | -11               | 6418               | -12               | 11229              |

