### 6.3 Outcome variables and study follow-up:

#### 6.3.1 Outcome variables

Effectiveness outcome variables of interest (definitions provided in **Appendix A**):

- **Primary outcome:** Vertebral fracture (algorithm adapted from Wright et al. 2019)
- **Secondary outcome:** Non-vertebral fracture

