## Appendix A

| # | VERO trial definitions  | Implementation in routine care   | Please see the following Google Drive for further details or any missing information:
https://drive.google.com/drive/folders/1WD618wrvvYIaxzflTcuK-VCnb6b-pV7usp-sharing   |  |
|---|---|--|--|--|
|   | Trial details - clinicaltrial.gov NCT01709110  |  | ICD-10 codes are not listed in this document because of excel cell size limitations and excessive number of ICD-10 codes. Full ICD-10 code lists will be available in the above Google Drive Folder (link above). ICD-9 to ICD-10 code conversions were completed using a SAS macro that implements forward/ backward mapping based on the CMS ICD-9 to ICD-10 mapping:
https://www.icer.org/data/icd9-icd-10-cm-and-pcs-crosswalk-general-equivalence-mapping.html |  |
|   | EXPOSURE vs. COMPARISON  |  | References/Rationale   | Color coding   |
| E | Exposure: 20 µg of teriparatide once daily   | Exposure: new use of Teriparatide (washout 730 days)

NDC Generic Name: TERIPARATIDE

NDC codes: 00002897101, 54868540600, 00002840001, 47781065289

Brand names: FORTEO

CPT/HCPGS Procedure Code: J3110   | Washout period - Criteria 20.1, 20.7   | Criteria   |

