|   | New radiographic vertebral fractures during a 24-month study period.

[Lateral spine radiographs were repeated at 12 and 24 months or early termination for new vertebral fractures. Additional unscheduled radiographs were done at any interim visit to detect new clinical vertebral fractures if the patient reported back pain clinically suggestive of a vertebral fracture.] | Measured 1 day after drug initiation:

Vertebral Fractures:
Algorithm include the following case-qualifying (CQ):

CQ = 1 Inpatient claim with primary diagnosis code
ICD9 dx: 805.x, 806.x, 733.13
ICD10 dx: S12.0xxA, S12.0xxB-S12.6xxA, S12.6xxB, S12.S22.0xxA, S22.0xxB (excluding "traumatic" and "burst" fractures which are high-energy fractures), M48.50XA, M80.08XA(excluding "stress" and "fatigue" fractures)
OR
CQ = 2 Non-inpatient claim with any diagnosis code [ICD9 dx: 805.x, 806.x, 733.13; ICD10 dx: S12.0xxA, S12.0xxB-S12.6xxA, S12.6xxB, S12.S22.0xxA, S22.0xxB (excluding "traumatic" and "burst" fractures), M48.50XA, M80.08XA(excluding "stress" and "fatigue" fractures)] AND procedure code HCPGS (22305, 22310, 22315, 22318, 22319, 22325-22328, 22510-22515, 22520-22525, 27200, 27202, 72291, 72292, 76012, 76013, 77082, 77085, 77086, S2360-S2363)
OR
CQ = 3 Non-inpatient claim with diagnosis code [ICD9 dx: 805.x, 806.x, 733.13; ICD10 dx: S12.0xxA, S12.0xxB-S12.6xxA, S12.6xxB, S12.S22.0xxA, S22.0xxB (excluding "traumatic" and "burst" fractures), M48.50XA, M80.08XA(excluding "stress" and "fatigue" fractures)] AND Physician E&M codes (HCPGS: 99024, 99058, 99201-99215, 99241-99245, 99271-99285, 99301-99335, 99366, 99385-99387, 99395-99404, 99429, 99449) AND, up to 10 days earlier (or on the same day), Outpatient claim of spine imaging codes (HCPGS: 72010-72159, 72240-72285, 72295) [] | Wright NC, Daigle SG, Melton ME, Delzell ES, Balasubramanian A, Curtis JR. The Design and Validation of a New Algorithm to Identify Incident Fractures in Administrative Claims Data. J Bone Miner Res. 2019 Oct;34(10):1798-1807. doi:10.1002/jbm.3807. Epub 2019 Aug 5. PMID: 31170317.  | Poor mapping or cannot be measured in claims                   |
|   | INCLUSION CRITERIA   |  |  | Can't be measured in claims but not important for the analysis |

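### As printed, entry and primary outcome share one ICD-9 list for vertebral fracture, but their ICD-10 lists differ in site (M80, S22, S32)

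*Combined protocol and SAP*

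**What the plan says.** Appendix A defines vertebral fracture twice.

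- **Entry (inclusion criterion 2).** A diagnosis between enrollment and 90 days before drug initiation, in any position and any care setting. The ICD-9 list is "ICD9 diagnosis codes: 805.x, 806.x, 733.13". The ICD-10 list is "ICD10 diagnosis codes: M48.4, M48.5, M80.x, S12.x, S22.x, S32.x". A list of procedure codes follows, with no AND or OR printed between the two. The section 5.3 flowchart carries this as "History of vertebral fracture (including from inception to 90 days").
- **Primary outcome.** Three case-qualifying rules, CQ1 to CQ3, each with the same ICD-9 codes as entry. The injury codes under ICD-10 read "ICD10 dx: S12.0xxA, S12.0xxB-S12.6xxA, S12.6xxB, S12.S22.0xxA, S22.0xxB". M48.50XA and M80.08XA are added, and high-energy, stress and fatigue fractures are excluded.

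A clean window sits between them. The note to criterion 2 says "We excluded patients with diagnosis of vertebral fractures from 89 days prior to and including the day of drug initiation", which the flowchart shows as "Vertebral fracture diagnosis excluded in the 90 days before cohort entry". No separate code list is printed for it.

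The header of Appendix A says "ICD-10 codes are not listed in this document because of excel cell size limitations and excessive number of ICD-10 codes" and refers the reader to an external folder for the full lists.

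**The concern.** The study sets out to replicate a trial in women with prior vertebral fracture whose endpoint is new vertebral fracture. The two definitions need not be identical, but they should agree on which sites count as vertebral. Under ICD-9 they do. Under ICD-10, as printed, they do not, and no reason is given.

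If the programs follow the print, both the target population and the endpoint change meaning with the coding version of the claim, which weakens the comparison with the trial. If the programs follow other lists, the registered appendix does not describe the study. Site matters in this plan because section 6.3.1 makes "Non-vertebral fracture" a separate secondary outcome.

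**Working it through.** **1. The plan's own figure.** The pooled power in section 10 is the stated figure that rests on the outcome definition. Events = 4,334 × 17.80/1,000 = 77.1452. Power = Φ(|ln 0.44| × √(77.1452/4) − 1.96) = Φ(0.821 × 4.392 − 1.96) = Φ(1.645) = 0.950. This matches the printed 0.950063363. It is internally sound, and the point below does not depend on it.

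**2. The printed lists side by side.**

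| Family | Entry | Outcome (CQ1 to CQ3) |
|---|---|---|
| ICD-9 | 805.x, 806.x, 733.13 | 805.x, 806.x, 733.13 |
| M80 | all | M80.08XA only |
| S22 | all | S22.0 only |
| S32 | all | none legible |
| S12 | all | S12.0 to S12.6 |
| M48.5 | all | M48.50XA only |
| M48.4 | all | none |

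The ICD-9 sets are identical. Every legible ICD-10 outcome code lies inside an entry category, but the reverse fails.

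**3. Which differences count.** The outcome's limits on encounter type, high-energy fractures and stress or fatigue fractures could be deliberate, so anything they might explain is left out; that may cover M48.4. The S12 difference is also left out, because the printed string is damaged next to it. M80, S22 and S32 remain. The plan itself shows that M80 has several subcodes: the osteoporosis criterion in the next row of Appendix A lists M80.00 to M80.08 separately.

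**4. What follows if programmed as printed.**

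- *Entry.* If a diagnosis code alone suffices (an OR with the procedure list, which is not printed), a woman can qualify on M80.00 to M80.07, or on an S22 code outside S22.0. The osteoporosis criterion would not screen out the former, since those M80 codes are on its own list. That step removes only 3 women in Optum and 18 in MarketScan (section 5.3).
- *Outcome.* An S32-coded fracture, which entry lists under a vertebral-fracture label, meets none of the three rules and cannot be a primary event.

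**5. Context on scale.** The documents give no date for the switch to ICD-10. Assume that starts from January 2016 fall in the ICD-10 period. From the matched table in Appendix B:

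- Optum: (233 + 228)/1,494 = 461/1,494 = 30.9%
- MarketScan: (202 + 221)/2,840 = 423/2,840 = 14.9%
- Pooled: (435 + 449)/4,334 = 884/4,334 = 20.4%
- By arm, pooled: risedronate 435/2,167 = 20.1%; teriparatide 449/2,167 = 20.7%

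These are women who start in that period, not women misclassified. Look-back runs from enrollment, so some may have qualified on earlier ICD-9 codes. Some earlier starters may have follow-up that runs into it.

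**The case against.** The strongest objection is that the printed ICD-10 strings may not be the operative ones. The header places the full lists outside the document, and the outcome string is visibly damaged (a fragment reads S12.S22.0xxA). The same string appears in all three rules, possibly copied, so its repetition is weak evidence. This stands as a limit: no programming error is shown. It does not remove the point. The appendix says that it does not list ICD-10 codes and then lists them, so a reader cannot tell which lists govern.

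A second objection is that a sensitive history definition with a specific outcome, adapted from a published algorithm, is a recognised design. That is fair for setting, diagnosis position, encounter type and energy of injury. It does not explain a difference in site that appears only under ICD-10.

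Four stronger readings are tempting and not supported:

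- *The clean window is a further contradiction*, because an S32 code on day 0 would exclude a woman and on day 1 would not be an event. This assumes that the window uses the entry list. A washout broader than the outcome is in any case legitimate, since its stated purpose is to separate incident from prevalent fractures.
- *The disputed codes decide most of the cohort*, because the history step removes 48,548 of 55,728 women (87.1%) in Optum and 103,348 of 115,587 (89.4%) in MarketScan. Those removals belong to the whole criterion, not to the codes at issue.
- *Between 20.4% and 46.2% of women are affected.* The higher figure adds all 2013 to 2015 starters: (884 + 559 + 561)/4,334 = 2,004/4,334. It is only a loose ceiling. Follow-up stops at 24 months (section 6.3.2), and median follow-up by arm is 148 to 234 days (section 9). Nor is 20.4% a lower bound for entry, given the look-back.
- *S32 fractures are counted as non-vertebral instead.* No code list for the secondary outcome is legible in the text, so this cannot be tested.

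**Conclusion.** The inconsistency holds as printed: one ICD-9 list, but ICD-10 lists that differ in site for M80, S22 and S32. Its consequences depend on the programs following the print. The entry consequence also depends on a diagnosis code being sufficient without a procedure. The absence of S32 is the natural reading of a partly garbled string, not a certainty.

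The numbers of wrongly admitted women and uncounted events cannot be derived. No bias between arms is shown; starts in 2016 or later are balanced after matching. No loss of power is shown either. What is at stake is whether population and endpoint keep one meaning across coding versions. That should be settled before results are produced. Confidence is medium: the printed difference is clear, but its effect on the programmed study is unknown.

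**What to change.** Before the comparative analysis (section 13 is blank):

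1. Compare the programmed ICD-10 lists for entry and outcome with the printed ones. If only the print is wrong, correct the appendix.
2. If the programs match the print, restrict the M80, S22 and S32 entry codes to their vertebral subcodes. Include the vertebral S32 and M48.5 initial-encounter codes in all three outcome rules, or state from the source algorithm why they are excluded. Keep the outcome's encounter-type, high-energy and stress or fatigue limits. State whether diagnoses and procedures are joined by AND or OR at entry.
3. State which list the clean window uses. It may be broader than the outcome list but must cover every outcome code.
4. Re-run flowchart, matching, balance, risk and power only if the programmed lists change. In either case, report entrants and primary events by ICD version, which would show the real size of the problem.

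The comparison and an appendix correction are cheap. If the programmed lists change, the steps reviewed in March and April 2021 must be repeated and the document registered on 04/30/2021 updated. Cohort and event counts would move by an unknown amount. Adding outcome codes would also depart further from the published algorithm.

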### 1.2 Intended aim(s)

To assess the effects of 24 months of treatment with teriparatide compared with risedronate on the incidence of new fractures in post-menopausal women with preexisting vertebral fractures, regardless of previous osteoporosis treatment.

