**Figure 1. Design Diagram – VERO TRIAL REPLICATION**

## 5. Cohort Identification

### 5.1 Cohort Summary

This study will involve a new user, parallel group, propensity score-matched, retrospective cohort design comparing injectable subcutaneous teriparatide (20 µg daily) to oral risedronate (35 mg weekly). The patients will be required to have continuous enrollment during a baseline period of 365 days before initiation of teriparatide or oral risedronate. We will restrict the analyses to women older than 45 with osteoporosis and history of vertebral fractures.

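### As printed, the history-of-vertebral-fracture criterion does not require a fracture diagnosis, so a procedure code alone appears enough to admit a woman

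*Combined protocol and SAP*

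**What the plan says.** Prior vertebral fracture defines the target population. Section 1.2 describes the trial population as "post-menopausal women with preexisting vertebral fractures", and Section 5.1 states: "We will restrict the analyses to women older than 45 with osteoporosis and history of vertebral fractures". The trial criterion to be emulated is "A minimum of 2 moderate (S02) or 1 severe (S03) vertebral fragility fractures", shown on radiographs (Appendix A, Inclusion 2).

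The claims version of Inclusion 2 sets one look-back, from enrollment to 90 days before initiation, and puts two lists under it. The first gives diagnosis codes, with the ICD-10 part reading "ICD10 diagnosis codes: M48.4, M48.5, M80.x, S12.x, S22.x, S32.x". The second is headed "Vertebral fracture procedures" and gives HCPCS and ICD procedure codes; the HCPCS part includes "27200, 27202, 72291, 72292, 76012, 76013, 77082, 77085, 77086". No AND or OR stands between the lists, and the codes have no descriptors.

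The flowchart in Section 5.3 applies this as criterion #3.1, "History of vertebral fracture (including from inception to 90 days", with one count per database and no split between diagnosis and procedure.

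**The concern.** If a procedure code is enough, women with no coded vertebral fracture can enter a cohort whose purpose is to represent women who have had one. The three codes 77082, 77085 and 77086 matter most. If they denote imaging that looks for a vertebral fracture, the claim shows that a woman was examined, not that a fracture was found. The documents do not say what these codes denote, so this is an assumption to confirm against the code list.

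At stake is whether the cohort matches the trial population, and whether the two arms contain the same mix of women with and without a diagnosed fracture. Correcting the outcome algorithm would not address this, because the issue is who enters.

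**Working it through.** **1. The same codes in two places (Appendix A).** The HCPCS list under Inclusion 2 is identical to the list in the second case-qualifying route of the primary outcome.

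- Outcome: the list counts only when joined by AND to a vertebral-fracture diagnosis code. The other two outcome routes also need a diagnosis code.
- Entry: the list stands beside the diagnosis list, with no stated requirement for a diagnosis.

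**2. How Appendix A treats unconnected lists.** Exclusion 2 prints renal osteodystrophy, osteomalacia, adrenal disorders, parathyroid disorders and malabsorption with no connector. The flowchart then removes women for each one separately, in rows #3.1 to #3.5 of the exclusions: 2, 11, 35, 60 and 27 in Optum; 1, 12, 62, 86 and 41 in MarketScan. Where two elements are both needed, the appendix writes AND. Alternatives are therefore the natural reading of Inclusion 2.

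**3. Whether a later step closes the gap.**

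- Inclusion #3.2 removes women with a recent fracture diagnosis. It does not require an older one.
- The osteoporosis criterion accepts a diagnosis or a listed treatment up to and including the day of initiation. Risedronate is on that treatment list and teriparatide is not, so as printed a risedronate starter passes on her index prescription. The step removes 3 women in Optum and 18 in MarketScan.
- The covariates in Appendix B include hip and femur fractures and other fractures. None records a vertebral-fracture diagnosis or the entry route.

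**4. Weight of the criterion (Section 5.3).**

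- Optum: 55,728 - 48,548 = 7,180, and 7,180/55,728 = 12.9% kept.
- MarketScan: 115,587 - 103,348 = 12,239, and 12,239/115,587 = 10.6% kept.

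These figures show how much depends on the criterion. They say nothing about how many women qualified on a procedure alone.

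**5. Power (Section 10).** Events = N x risk/1,000. Power = Phi( sqrt(events x 0.25) x |ln HR| - 1.96 ), with HR 0.44 and two-sided alpha 0.05. The plan's figures reproduce:

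- Pooled: 4,334 x 17.80/1,000 = 77.1452 events; power 0.9501 (stated 0.9501).
- Optum: 1,494 x 15.90/1,000 = 23.7546 events; power 0.5162 (stated 0.5163).
- MarketScan: 2,840 x 18.90/1,000 = 53.676 events; power 0.8526 (stated 0.8526).

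Now assume that a share f of the pooled matched women is procedure-only and is dropped, with q times the fracture risk of the others. The remaining events are 77.1452 x (1 - f)/((1 - f) + f x q).

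| f | q = 1: events, power | q = 0.5: events, power | q = 0: events, power |
|---|---|---|---|
| 10% | 69.4, 0.928 | 73.1, 0.939 | 77.1, 0.950 |
| 30% | 54.0, 0.855 | 63.5, 0.905 | 77.1, 0.950 |
| 50% | 38.6, 0.722 | 51.4, 0.837 | 77.1, 0.950 |

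Both f and q are assumptions; the documents give neither. A fresh match would also change the numbers somewhat.

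**The case against.** **The connector is not printed.** Appendix A does print OR in the osteoporosis criterion, so silence in Inclusion 2 does not settle the rule. Appendix A also points to an external folder for missing detail, which may hold the answer. This stands as a limit: alternatives is the natural reading, not a stated rule. But if a diagnosis was meant to be required, the protocol does not say so.

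**The meaning of the three codes comes from outside the documents.** This also stands. The mismatch between entry and outcome does not depend on it, because it concerns the whole procedure list.

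**A reader might infer that imaged-only women sit mainly in the risedronate arm and pull the HR towards 1.** The documents do not support this. Before matching, teriparatide starters had more DXA tests: 0.74 against 0.57 in Optum and 0.50 against 0.41 in MarketScan. The DXA count is in the PS model, and its means are equal after matching (0.73 in both Optum arms, 0.49 in both MarketScan arms). That is not a full answer either, because the documents do not say whether the three codes count as DXA tests, and scans from early in the look-back may fall outside the covariate window.

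The arithmetic shows how far the direction depends on assumption. Let s_t and s_r be the procedure-only shares under teriparatide and risedronate, let r be these women's relative risk, and suppose a true HR of 0.44 in both kinds of women. The HR is then multiplied by about (1 - s_t(1 - r))/(1 - s_r(1 - r)).

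- s_r = 10%, s_t = 5%, r = 0.5: 0.975/0.95 = 1.03, HR 0.45.
- s_r = 30%, s_t = 5%, r = 0.3: 0.965/0.79 = 1.22, HR 0.54.
- The same two cases with the shares exchanged: factors 0.97 and 0.82, HR 0.43 and 0.36.
- Equal shares: factor 1, no bias.

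Nothing in the documents chooses between these cases.

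**Requiring a diagnosis may drop true cases.** A woman treated for a fracture whose diagnosis was not captured would be lost. This is a real cost and is taken into account in the fix.

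**Conclusion.** The point holds in this form. Inclusion 2 does not require a fracture diagnosis; on its natural reading, a procedure code alone admits a woman with no coded vertebral fracture. Entry is then looser than the outcome on identical HCPCS codes, no later step requires a fracture diagnosis, and no printed covariate separates the two routes.

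The conclusion that imaged-only women can enter rests on one further assumption, that 77082, 77085 and 77086 denote vertebral-fracture assessment. A reader might also infer that such women did enter. No count shows that even one did, and the size and direction of any effect on the HR cannot be determined. Nor is the power calculation wrong: it uses the overall risk in the cohort as built, and its arithmetic reproduces.

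The criterion should be corrected before the comparative analysis. Section 13 is still blank in this version, so that is possible without knowledge of results.

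**What to change.** - Require at least one vertebral-fracture diagnosis code before day -90 for Inclusion 2, so that no procedure code qualifies alone, and state this rule in Appendix A.
- Confirm against the code list what 77082, 77085 and 77086 denote.
- Report, by arm and database, how many women had qualified on a procedure code alone.
- Re-run the flowchart from row #3.1, the PS match and the power table before the comparative analysis.
- Keep the current definition as a sensitivity analysis, which retains women with a fracture treatment but no captured diagnosis.

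The cost is one code-list edit, a re-run and a smaller cohort. Pooled power stays at 0.950 if the dropped women contribute no events, and falls to 0.928 if 10% are dropped at equal risk. It falls further only if the procedure-only share is large, in which case the change matters most.
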